- k For subjects who receive non-trial SARS-CoV-2 vaccinations there will be no sampling in subsequent visits. Information about these vaccinations may be received outside of a planned visit and can be collected remotely, e.g., by phone. In such cases information on physical examination and vital signs can be skipped. However, AEs that occurred prior to administration of non-trial vaccine must be enquired and should be recorded as stated in footnote "i".
- Record any non-trial SARS-CoV-2 vaccinations that trial subjects receive during the trial in the CRF until the last trial visit.

Abbreviations: AE = adverse event; AESI = adverse event of special interest; CMI = cell mediated immunity; CRF = case report form; d = day; ELISA = enzyme-linked immunosorbent assay; EOT = end of trial; h = hour(s); IMP = investigational medicinal product; inj. = (IMP) injection; NAAT = nucleic acid amplification-based test; NATAB = neutralizing antibody titers and antibody binding; SAE = serious adverse event; SARS-CoV-2 = the virus leading to COVID-19; SoA = schedule of activities; WOCBP = women of childbearing potential.

		Page 12
BioNTech SE	Clinical Trial Protocol	Versio
Confidential	BNIT162 14	VEISIO
Connuential	DINT 102-14	Dete: 00 I

Page 12 of 91 Version: 4.0 Date: 20 JAN 2022

Table 2: Schedule of events for Immunology Subgroup of Group B (with two injections of Comirnaty) h

Activity	Visit 0	Visit 1	Visit 2	Visit 3	Visit 4	Visit 5	Visit 6 ^{I, m}	Visit 7 ^{I, m, o}	Early termination
Week(s)			1	3	4	7	12	26	
Day	-30 to -1	1	8+2	22±3	29+7	50±7	85±10	182±20	
	(Screening)	(Day of inj. 1; pre-dose except IMP injection)	(~7 d post inj. 1)	(~21 d post inj. 1; pre-dose except IMP injection)	(~7 d post inj. 2)	(~28 d post inj. 2)	(~63 d post inj. 2)	(~161 d post inj. 2 EOT Visit)	
Collect informed consent	Х						X m	X m	
Assess inclusion/exclusion criteria compliance	Х	X (review)							
Collect demographic and medical history	Х	X (update)							
Physical examination	Х	X a	X a	X a	X a			X a	X a
Vital signs, body weight ^b	Х	Хc		Хc					
Urine pregnancy test for WOCBP	Х	х		х				х	х
Blood draw for clinical laboratory (15 mL) ^d	Х								
Allocation to IMP		х							
IMP injection, then observe subjects for ~1 h		х		X ^h					
Subject hotline availability	Start	=>	=>	=>	=>	=>	=>	End	(End)
Oral swabs for NAAT-based SARS-CoV-2 for screening ^f	X e	X e							
Oral swab for NAAT-based SARS-CoV-2 testing for surveillance			х	x	х	Х	х	х	x

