Record non-trial SARS-CoV-2 vaccinations ^j		Х	х	Х	Х	х	х	Х	х

Note: The SoA allows for ad hoc SARS-CoV-2 testing for symptomatic or asymptomatic subjects.

- a Brief (symptom-directed) physical examination; no height measurement.
- b Vital signs: systolic/diastolic blood pressure, pulse rate, respiratory rate, and body temperature; body weight only at Visit 0.
- c Vital signs pre-dose on days with IMP injection.
- d Clinical laboratory tests: (Chemistry) alkaline phosphatase, creatinine, ferritin, C-reactive protein, albumin, alanine aminotransferase, amylase, aspartate aminotransferase, gamma glutamyl transpeptidase, total bilirubin, blood urea nitrogen, glucose, lipase, sodium, potassium, calcium; (Hematology) hemoglobin, hematocrit, red blood cell count, white blood cell count and differential (neutrophils, lymphocytes, monocytes, eosinophils, basophils), platelet count. Only in women who are not WOCBP (to confirm post-menopausal status): follicle stimulating hormone at Visit 0. Also to be performed if clinically indicated at any visit.
- e Oral swab for SARS-CoV-2 testing either on Day -1 or at Visit 1 on Day 1.
- f Will be tested within 24 h either at a central laboratory or a "point of care" device at the trial site or a local laboratory of the trial site.
- g Swabs will only be analyzed (sequenced) if serum nucleocapsid protein ELISA testing and/or NAAT-based SARS-CoV-2 testing detects SARS-CoV-2 (with or without symptoms). Oral swabs for SARS-CoV-2 sequencing must be collected at the same day/time (±30 minutes) as the oral swabs for NAAT-based SARS-CoV-2 for screening/surveillance.
- h Only, AESIs, SAEs, and all AEs linked to confirmed COVID-19 cases will be recorded until the end of trial. For subjects who receive non-trial SARS-CoV-2 vaccinations, the AEs expected to be captured after these vaccinations are within the frame of post-marketing safety data reporting (see Section 8.3.1).
- i For subjects who receive non-trial SARS-CoV-2 vaccinations there will be no sampling in subsequent visits. Information about these vaccinations may be received outside of a planned visit and can be collected remotely, e.g., by phone. In such cases information on physical examination and vital signs can be skipped. However, AEs that occurred prior to administration of non-trial vaccine must be enquired and should be recorded as stated in footnote "i".

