7.2 Trial subject discontinuation or withdrawal from the trial

A trial subject may withdraw from the trial at any time at his/her own request or may be discontinued from the trial at any time at the discretion of the investigator for safety, behavioral, compliance, or administrative reasons. Withdrawals are expected to be uncommon.

Reasons for discontinuation from the trial include the following:

- Refused further trial procedures
- Lost to follow-up
- Death
- Trial terminated by sponsor
- SAEs thought related to the vaccine
- Trial subject request
- Investigator request
- Important protocol deviation per the investigator after consultation with the Medical Monitor
- A Group B transplant subject who receives a non-trial SARS-CoV-2 vaccination

If the trial subject withdraws consent for data processing, the sponsor may retain and continue to use any data collected before such a withdrawal of consent.

For trial subjects who withdraw consent, the investigator must clarify whether consent for research sample storage/processing (if given) is also withdrawn. If yes, then they must be informed that any research samples collected will be destroyed. The investigator must document research sample destruction in the Investigator's Site File (ISF) and inform the sponsor about the withdrawal of consent immediately.

If possible, permanently discontinued trial subjects will complete all assessments planned for the Early Termination Visit.

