6.1. General considerations

No formal statistical testing will be done.

Unless otherwise specified, analyses will be based on data pooled across all study sites within the BNT162-14 trial.

Data assessed after a vaccination with a non-trial SARS-CoV-2 vaccine will be excluded from all statistical analyses (tables and listings) accordingly.

Notes:

- Data assessed on the same day as the non-trial vaccination will remain in the analysis.
- If the date of non-trial vaccination is missing, but month and year information is available, data assessed after the last day of the respective month will be excluded from statistical analysis.

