6.5. Secondary endpoint analyses

Secondary endpoints are neutralizing antibody titers and antibody titers (ELISA) to recombinant S1 and RBD protein derived from reference and SARS-CoV-2 variant B.1.351 (B.1.351 for Group A only) and SARS-CoV-2 functional cross-neutralization of variant B.1.351 to reference strain (for Group A only). All secondary analyses will be performed using the IMM and possibly additionally the IMMPP population, see Section 5.1.

Any COVID-19 vaccination that a subject received outside of this trial will be considered as concurrent event and all immunogenicity data assessed beyond this event will be excluded from the immunogenicity analyses.

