6.6. Sensitivity analyses

Sensitivity analyses of immunogenicity endpoints (see Section 6.5) may be conducted as appropriate by excluding subjects with a SARS-CoV-2 infection during the BNT162-14 trial.

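### When the day of a non-trial SARS-CoV-2 vaccination is unknown, the SAP cuts the data at the end of that month and can keep a titer drawn after the extra dose

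*SAP*

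**What the plan says.** SAP 6.1 sets the general rule: "Data assessed after a vaccination with a non-trial SARS-CoV-2 vaccine will be excluded from all statistical analyses (tables and listings) accordingly". Two notes follow. The first says "Data assessed on the same day as the non-trial vaccination will remain in the analysis". The second covers a date with the day missing but the month and year known, and there "data assessed after the last day of the respective month will be excluded from statistical analysis". Nothing is said about a date whose month is also missing.

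SAP 6.5 treats a COVID-19 vaccination outside the trial as a concurrent event, after which "all immunogenicity data assessed beyond this event will be excluded from the immunogenicity analyses". It has no partial-date rule of its own, so the 6.1 convention applies to titers as well.

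The protocol also acts on sampling. Footnotes to the schedules in Section 1.3 state: "For subjects who receive non-trial SARS-CoV-2 vaccinations there will be no sampling in subsequent visits". The footnote is marked on Visits 6 and 7 in Tables 1 and 2, on Visits 11 and 12 in Table 2a, and on Visit 7 only in Table 3. It is not marked on the Early Termination column of any table. Sites are also told: "Record any non-trial SARS-CoV-2 vaccinations that trial subjects receive during the trial in the CRF until the last trial visit".

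The only sensitivity analysis for immunogenicity (SAP 6.6) is optional and concerns "excluding subjects with a SARS-CoV-2 infection during the BNT162-14 trial". It does not address uncertain vaccination dates.

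**The concern.** The exclusion exists so that a response to an outside dose is not credited to the trial vaccine. For a partial date, the last-day cut treats the vaccination as having happened as late as it could have. Any sample drawn that month after the true vaccination then counts as trial-vaccine response in the GMT, the GMFR and the seroconversion rate.

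The error has one direction. A titer drawn after an extra dose is expected to be raised, so late summaries, which describe durability, can only be pushed up. The rule also ignores information that the trial collects. Suppose a Table 3 subject says at Visit 6 that an outside dose was given earlier that month, but does not know the day. Blood may still be drawn, because the footnote is not marked on that visit. The sample is known to follow the dose, yet the rule keeps it.

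**Working it through.** The plan states no figure on this point, so there is none to reproduce. The check has four steps.

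**1. Longest retained span.** For a month of L days and a vaccination on day d, the last retained day is L, so the retained post-vaccination span is L − d. It is longest at d = 1:

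- L = 31: 30 days
- L = 30: 29 days
- L = 29: 28 days
- L = 28: 27 days

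**2. What a fixed cut gets wrong if nothing else is known.** Assume that vaccination day and sampling day are independent and uniform within the month. The share of same-month samples that follow the vaccination is (L − 1)/(2L). For L = 31 this is 30/62 = 48%. The share that follow by 7 days or more is (24 × 25/2)/31² = 300/961 = 31%. Either fixed cut, first day or last day, would then misclassify about half of these samples. Visit records are what can do better.

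**3. Where a titer can actually be drawn after the dose.** The antibody draws in the schedules, set against the stop-sampling footnote:

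| Schedule | Antibody draws after injection | Footnote marked on |
|---|---|---|
| Table 1 (Group A) | Visits 2, 4, 6, 7; Early Termination | Visits 6, 7 |
| Table 2 (Group B immunology subgroup) | Visits 2 to 7; Early Termination | Visits 6, 7 |
| Table 2a (transplant, injection 2) | Visits 9 to 12; Early Termination | Visits 11, 12 |
| Table 3 (rest of Group B) | Visits 2 to 7; Early Termination | Visit 7 |

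The widest late gap is in Table 3, which covers up to 459 − 129 = 330 subjects and leaves Weeks 7 and 12 unmarked. Where the footnote does apply, it works only if the site knows of the dose. The footnotes themselves accept that this information may arrive outside a planned visit.

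A 30-day span seldom holds more than one late titer. Nominal Days 50 and 85 are 35 days apart, and Visits 6 and 7 are at least (182 − 20) − (85 + 10) = 67 days apart even at the edges of their windows. Visits 5 and 6 can come as close as (85 − 10) − (50 + 7) = 18 days, so the limit of one holds usually, not always.

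**4. Effect of one retained titer.** If m of n titers are each inflated k-fold, the GMT is multiplied by k^(m/n). Neither k nor m is in the documents. With m = 1 and k assumed to lie between 2 and 20:

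| Summary | n | k = 2 | k = 20 |
|---|---|---|---|
| Group A, Comirnaty (90 × 1/3) | 30 | +2.3% | +10.5% |
| Group A, BNT162b2s01 (90 × 2/3) | 60 | +1.2% | +5.1% |
| Table 3 subjects | 330 | +0.2% | +0.9% |
| Group B, total | 459 | +0.2% | +0.7% |

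One false seroconverter adds 1/30 = 3.3 percentage points at n = 30 and 1/459 = 0.2 points at n = 459.

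**The case against.** The strongest reply is that most such titers are never drawn. Sampling stops after a non-trial vaccination, and vaccinations are recorded at visits. If a subject was sampled during the month and reported no dose, the dose more likely came afterwards, and the last-day cut then correctly keeps a valid titer. This stands. It rules out reading the rule as leaving 30 days of contaminated titers in every partial-date case. It does not help where the dose was disclosed and blood was drawn anyway, or where nobody documented the subject's status.

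Three stronger readings are tempting but not supported:

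- **That SAP 6.1 contradicts SAP 6.5.** Section 6.5 states the principle and is silent on partial dates; 6.1 supplies the convention. The convention works against the aim of 6.5, but the two texts do not conflict.
- **That the transplant subjects are the main problem.** With n = 15, one titer boosted 2- to 20-fold would raise the GMT by 4.7% to 22.1%, and one false seroconverter would add 6.7 points. But protocol Section 7.2 lists "A Group B transplant subject who receives a non-trial SARS-CoV-2 vaccination" among the reasons for discontinuation, and the footnotes in Tables 2 and 2a stop the later draws. An Early Termination draw remains possible, but SAP 6.1.1 bases summaries on scheduled visits and does not say how that visit is mapped. The titer may reach only the listings.
- **That all late titers from Week 7 onward are exposed in every group.** Group A has no Week 7 antibody draw, and its Week 12 and Week 26 draws carry the footnote.

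**Conclusion.** The point holds as a minor one. The partial-date rule can keep a titer drawn up to 30 days after a non-trial vaccination, even when the visit record shows the order of events, and no planned sensitivity analysis would reveal it. The bias is upward.

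The expected size is small. Where the footnote gap is widest, the denominators are large and one retained titer moves the GMT by under 1%. In Group A the effect per titer is larger, but late exposure there depends on late disclosure or an Early Termination draw. All effect sizes rest on the assumed 2- to 20-fold boost and are per affected subject; the number affected is unknown. The trial is descriptive with no hypothesis under test, so no formal conclusion depends on this.

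**What to change.** Replace the partial-date note in SAP 6.1, for immunogenicity data only, with wording such as:

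> If only month and year are known, immunogenicity data assessed on or after the first day of that month are excluded, except data up to and including the last visit at which the subject was documented as not yet vaccinated. If the month is also missing, data after the last documented unvaccinated visit are excluded.

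The last-day cut can stay for safety data, where it errs towards keeping events.

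The cost is a short SAP edit and a derivation that uses vaccination status by visit. Because documented unvaccinated visits are protected, the new rule differs from the present one only when a dose had been disclosed or status was not documented. A few genuine pre-vaccination titers may be lost. That costs a little precision, whereas the present rule risks crediting another vaccine's response to the trial vaccine.

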6.1.1. Tables and listings

Tables

In general, data will be summarized as follows:

- Group A by vaccine [Comirnaty[®], BNT162b2s01], and total
- Group A subjects having received Comirnaty[®] by HIV infection status
- Group A subjects having received BNT162b2s01 by HIV infection status
- Group B by transplant status, and total
- Group B immunology subset by transplant status, and total

Descriptive summary tables and figures will be based on scheduled visits.

Continuous variables will be summarized using the following descriptive statistics: number of subjects with non-missing data (n), mean, standard deviation (SD), median, minimum (min) and maximum (max).

Descriptive statistics of titer and fold rise of titer will additionally include geometric mean and its two-sided 95% confidence interval (CI). The geometric mean titer (GMT) is calculated as the mean of the logarithm of the functional antibody titers, backtransformed into the original scale. Two-sided CIs will be obtained by calculating CIs using t-distribution for the mean of the logarithmically transformed assay results and transforming the limits back to the original scale.

Geometric mean fold rise (GMFR) is calculated as the mean of the difference of logarithmically transformed assay results (post vaccination time point – pre vaccination time point) and back-transformed into the original scale. Two-sided CIs will be obtained by calculating CIs using Student's t-distribution for the mean difference of the

logarithmically transformed assay results and transforming the limits back to the original scale.

Categorical variables will be summarized presenting absolute and relative frequencies (n and %) of subjects in each category (including the category 'missing' if applicable). Percentages will be calculated based on the number of subjects in the respective analysis set (N) as denominator if not stated differently. Percentages may be presented with exact 95% Clopper-Pearson CIs.

SDs and CIs will only be calculated if values from at least 3 subjects are available.

Listings

Important Case Report Form (CRF) data and all relevant generated and transformed variables together with the original data items will be listed. Separate listings will be provided for Group A and B and immunology subset of Group B. Listings will be sorted first by vaccine (for Group A), subgroup (HIV-positive subjects for Group A, transplant subjects for Group B or immunology subset of Group B), site ID and by subject number and finally, if applicable, by visit number and/or a relevant date (e.g., date of onset of AE).

Programming

SAS[®] (version 9.4 or higher) programming will be performed according to Staburo GmbH standards as defined in SOP001_PROGRAMMING [1] and related work instructions. Special attention will be paid to planning and performance of quality control measures as documented in the quality control plan for the analysis of this study (see also SOP002_PROGRAM_QC [2]).

Analysis sets

The SCR will be used for disposition. The SAF will be used for analysis of safety and adverse events data. Some analyses of the adverse events will be repeated for Group B using the SAFB if the SAF and the SAFB sets differ. The IMM will be used for the analysis of immunogenicity data. The immunogenicity analyses may be repeated using the IMMPP if the two analysis sets differ significantly. This will be decided at the data review meeting.

Data of subjects who failed to complete all visits of the trial (dropout or withdrawal) will be reported as far as their data is available.

6.1.2. Definitions and derivations

Unscheduled visits

Unscheduled visits will not be included in the summary tables but will be included in the listings.

Variables

Unless otherwise specified, **baseline** is defined as last value prior to first injection of IMP (Dose 1) given in this BNT162-14 trial on Day 1, including unscheduled visits.

Change from baseline will be calculated as follows:

• Change from baseline = post-baseline assessment value – baseline assessment value.

Duration [days] will be calculated as follows:

• Duration [days] = last observation date – first observation date + 1

Time from first injection (Dose 1) to first reaction will be calculated as follows: Time from first injection to first reaction [days] = first reaction date – date of first injection (Dose 1) + 1

Time from first reaction to last reaction will be calculated as follows:

Time from first to last reaction [days] = last reaction date – first reaction date + 1

Days since last injection will be calculated as follows:

Days since last injection = onset date of AE – date of last injection +1

For conversion of days to months or years the following rules will be applied:

- 1 month = 30.25 days
- 1 year = 365.25 days

Study Day and are defined as follows:

- Study day:
 - If study date < date of first injection (Dose 1), then study day = study date date of first injection
 - If study date >= date of first injection (Dose 1), then study day = study date date of first injection + 1

Fold rise will be calculated as follows:

• Fold rise = post-dose value / baseline value

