Oral swab for SARS-CoV-2 sequencing ^g	X e	X e	Х	х	Х	Х	Х	х	х
Blood draws for NATAB and nucleocapsid protein testing (15 mL)		x	х	x	х	х	х	х	x
Blood draws for CMI (100 mL each)		х	Х		X ^h		Х	x	х
Issue/collect subject diaries		X (issue)	X (collect)	X (issue) ^h	X (collect) h				

Activity	Visit 0	Visit 1	Visit 2	Visit 3	Visit 4	Visit 5	Visit 6 ^{I, m}	Visit 7 ^{I, m, o}	Early termination
Week(s)			1	3	4	7	12	26	
Day	-30 to -1	1	8+2	22±3	29+7	50±7	85±10	182±20	
	(Screening)	(Day of inj. 1; pre-dose except IMP injection)	(~7 d post inj. 1)	(~21 d post inj. 1; pre-dose except IMP injection)	(~7 d post inj. 2)	(~28 d post inj. 2)	(~63 d post inj. 2)	(~161 d post inj. 2 EOT Visit)	
Subjects report daily reactogenicity (incl. body temperature) in their diary for 7 days post each vaccination		X (post- dose) ⁱ	х	X (post- dose) ^h	X ^h				
Record AEs since last visit		х	Х	х	Х	X ^k	Хj	Хj	Х
Record pregnancies		=>	=>	=>	=>	=>	=>	End	(End)
Record concomitant medication		х	Х	Х	Х	X p	X n	X ⁿ	X ⁿ

Note: The SoA allows for ad hoc SARS-CoV-2 testing for symptomatic or asymptomatic subjects.

a Brief (symptom-directed) physical examination; no height measurement.

b Vital signs: systolic/diastolic blood pressure, pulse rate, respiratory rate, and body temperature; body weight only at Visit 0.

c Vital signs pre-dose on days with IMP injection.

- d Clinical laboratory tests: (Chemistry) alkaline phosphatase, creatinine, ferritin, C-reactive protein, albumin, alanine aminotransferase, amylase, aspartate aminotransferase, gamma glutamyl transpeptidase, total bilirubin, blood urea nitrogen, glucose, lipase, sodium, potassium, calcium; (Hematology) hemoglobin, hematocrit, red blood cell count, white blood cell count and differential (neutrophils, lymphocytes, monocytes, eosinophils, basophils), platelet count. Only in women who are not WOCBP (to confirm post-menopausal status): follicle stimulating hormone at Visit 0. Also to be performed if clinically indicated at any visit.
- e Oral swab for SARS-CoV-2 testing either on Day -1 or at Visit 1 on Day 1.

f Will be tested within 24 h either at a central laboratory or a "point of care" device at the trial site or a local laboratory of the trial site.

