8.2.3 Clinical laboratory tests

See Section 10.2 for the list of clinical laboratory tests to be performed at baseline and the limited times given in the SoA (Section 1.3).

The investigator must review the laboratory report, document this review with signature and date.

All laboratory tests with values considered clinically significantly abnormal during participation in the trial should be repeated until the values return to normal or baseline or are no longer considered clinically significant by the investigator.

If such values do not return to normal/baseline within a period of time judged reasonable by the investigator, the etiology should be identified and the sponsor notified.

All protocol-required clinical laboratory tests (see Section 10.2) must be conducted in accordance with the central laboratory standard.

If laboratory values from non-protocol-specified laboratory assessments performed at the laboratory require a change in trial subject management or are considered clinically significant by the investigator (e.g., SAE, AE), then the results must be recorded in the CRF.

BioNTech SE	
Confidential	

Clinical Trial Protocol BNT162-14

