6.8.2. Laboratory assessments

Definition

Clinical laboratory data to be summarized includes hematology, clinical chemistry, and urinalysis and will be assessed at the time-points indicated in Tables 1, 2, 2a, and 3 of the protocol.

The following clinical laboratory variables will be assessed:

Hematology

Hemoglobin, hematocrit, red blood cell count, white blood cell count and differential (neutrophils, lymphocytes, monocytes, eosinophils, basophils), platelet count.

Clinical chemistry

Alkaline phosphatase, creatinine, ferritin, C-reactive protein, albumin, alanine aminotransferase, amylase, aspartate aminotransferase, gamma glutamyl transpeptidase, total bilirubin, blood urea nitrogen, glucose, lipase, sodium, potassium, calcium.

Follicle-stimulating hormone: In women only.

Urinalysis

Dipstick: glucose, bilirubin, ketone, specific gravity (1 mL \triangleq 1 g), blood, pH, protein, urobilinogen, nitrite, and leukocytes.

Microscopic urinalysis: If warranted by dipstick results, urine sediment will be microscopically examined for presence of red blood cells, white blood cells, casts, crystals, epithelial cells, and bacteria.

All laboratory tests are classified as normal or lower or higher than reference range (abnormal). All abnormal laboratory tests will be classified by the investigator as clinically significant (CS) or not clinically significant (NCS).

Abnormal lymphocytes data will be categorized as defined in table 7 in the protocol as Grade 1 (mild), Grade 2 (moderate), Grade 3 (severe), and Grade 4 (potentially life-threatening).

Analysis

Clinical laboratory variables at each time-point and its change from baseline to each post-baseline time-point (for continuous variables and if applicable) will be summarized using descriptive summary statistics for each parameter.

Number and percentage of subjects with low, normal and high clinical laboratory values at each time-point will be summarized for each parameter. The same table will be provided for the grading scheme (grades mild, moderate, severe and life threatening) for lymphocytes.

The number and percentage of subjects with CS abnormal, abnormal (NCS), normal and missing values will be summarized for each parameter.

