Clinical laboratory values for each parameter will be summarized using shift tables from baseline to worst post-baseline value with respect to reference range values (low, normal, high), if applicable. Worst post-baseline might be in both directions. Each subject may be counted in the parameter high and in the parameter low category. A subject will only be counted in the normal category if all post-baseline values are normal. If several post-baseline values are considered as worst post-baseline value, the first one is taken.

All clinical laboratory data will be presented in the data listings along with normal ranges abnormal clinical laboratory values will be flagged in the listing.

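### Under the scheduled-visits rule, the laboratory shift to worst post-baseline value can count a subject as normal despite an abnormal result at an unscheduled visit

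*SAP*

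**What the plan says.** Two general rules in the SAP limit what enters a table. Section 6.1.1: "Descriptive summary tables and figures will be based on scheduled visits". Section 6.1.2: "Unscheduled visits will not be included in the summary tables but will be included in the listings". The same section defines baseline as the last value before the first injection and expressly allows that value to come from an unscheduled visit.

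SAP 6.8.2 says that laboratory variables "will be assessed at the time-points indicated in Tables 1, 2, 2a, and 3 of the protocol", and that values for each parameter "will be summarized using shift tables from baseline to worst post-baseline value", classed against the reference range. It adds: "A subject will only be counted in the normal category if all post-baseline values are normal". It does not mention unscheduled or repeat tests. Appendix 1, on departures from the protocol's analyses, does not mention them either.

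The protocol expects off-schedule results. Section 1.3 lets the investigator add unplanned visits. Section 8.2.3 says that clinically significant abnormal tests "should be repeated until the values return to normal or baseline" or are no longer judged significant. Section 8.11 allows extra samples after adverse events. For the Group B immunology subset, Table 2 footnote d says of the laboratory panel: "Also to be performed if clinically indicated at any visit".

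**The concern.** A worst-value table exists to catch the most extreme result, whenever it occurred. If its input is cut to scheduled visits, it reports the worst scheduled value under a label that promises more. Leaving values out can only keep a subject's worst value the same or make it look better, so any error in this table runs one way.

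The two ends of the shift also follow different rules, since an unscheduled value can serve as baseline but not as worst value. At stake is whether a reader can trust the normal-to-normal cells. The case is foreseeable here: immune thrombocytopenia is an adverse event of special interest (Protocol 8.3.8), and a platelet count prompted by symptoms may well be taken between planned visits.

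**Working it through.** **Step 1. Scheduled laboratory draws (Protocol 1.3).**

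| Population | Scheduled safety-laboratory draws | Post-baseline |
|---|---|---|
| Group A (Table 1) | Visits 0, 1, 4, 7, plus early termination | Visit 4 (Day 29±7), Visit 7 (Day 182±20), early termination |
| Immunology subset (Table 2) | Visit 0 | none |
| Transplant subjects, injection 2 (Table 2a) | Visits 8, 9, 10, haematology only | all three, being after Dose 1 |

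**Step 2. Check the counts against the blood volumes in Protocol 8.11.** Planned volume = laboratory draws × 15 mL + antibody draws × 15 mL + cell-mediated immunity draws × 120 mL (Group A) or 100 mL (Group B).

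- Group A: 4×15 + 5×15 + 4×120 = 60 + 75 + 480 = 615 mL (stated: about 615).
- Immunology subset: 1×15 + 7×15 + 5×100 = 15 + 105 + 500 = 620 mL (stated: about 620).
- Other Group B: 1×15 + 7×15 = 120 mL (stated: about 120).

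All three agree, so the sparse schedule is intended and is not an artefact of a broken table.

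**Step 3. Subjects with no scheduled post-baseline draw.** From Protocol 4.1, the immunology subset is 36 + 30 + 15 + 48 = 129, of whom 15 are transplant subjects: 129 − 15 = 114. Any post-baseline laboratory result in these 114 must come from clinically indicated testing. SAP 6.8 nevertheless plans laboratory summaries for them.

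**Step 4. Apply the rules to one hypothetical subject.** Take a Group A subject with normal platelets at baseline, Visit 4 and Visit 7, and a low count at an unplanned visit around Day 14.

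- Scheduled-visits rule (6.1.1, 6.1.2): the values used are normal and normal, so the shift is normal to normal.
- The 6.8.2 condition on the normal category: not all post-baseline values are normal, so the shift is normal to low.

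The SAP gives two answers for the same subject and does not say which rule prevails.

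**Step 5. Possible size (illustration only).** The documents do not give the share q of subjects whose worst value appears only at an unscheduled visit, so q is assumed over a range. With n = 90 (the Group A maximum), expected misclassified = 90q, and the probability of at least one = 1 − (1 − q)^90.

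| Assumed q | Expected subjects | P(at least one) |
|---|---|---|
| 1% | 0.9 | 0.60 |
| 2% | 1.8 | 0.84 |
| 5% | 4.5 | 0.99 |
| 10% | 9.0 | >0.99 |

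**The case against.** The strongest reply is that the condition on the normal category in 6.8.2 already reaches every value, and that a specific rule overrides a general one. That reading is possible, but the SAP does not state it. A programmer following 6.1.1 and 6.1.2 would filter the data first.

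A second reply is that nothing is lost. All laboratory data are listed with abnormal values flagged (SAP 6.8.2), and the safety review committee sees laboratory data (Protocol 10.1.5). Clinically significant findings are to be documented as adverse events (Protocol 10.3.1.7), whose tables are built on onset time, not on visit (SAP 6.4.3). This largely stands and limits the consequence. It is not a complete safeguard: from Visit 5 in Group A and Visit 6 in the non-transplant immunology subset, recording narrows to related, special-interest, serious and COVID-19-linked events (Protocol 1.3). Listings also do not correct a table.

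A reader might infer more than the documents support:

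- **That all post-baseline laboratory data in the 114 are excluded.** The rule names unscheduled visits. A clinically indicated test at a planned visit, such as Visit 2 at Day 8 to 10, is not plainly barred. The SAP is silent on it.
- **That unscheduled tests are where the worst values lie.** Repeats continue until values recover, so the scheduled result that prompted them may itself be the worst. Worst values can occur off schedule; the documents do not show that they usually do.
- **That early-termination results are dropped.** Early termination is a column of the Group A schedule with a laboratory draw, and SAP 6.1.1 says that available data from dropouts are reported.
- **That other laboratory tables share the fault.** SAP 6.8.2 has no worst-grade laboratory table, and its lymphocyte grades follow the by-time-point format. Scheduled visits are a normal basis for by-visit tables.

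**Conclusion.** The point holds for the baseline-to-worst-post-baseline shift table, and for the count of clinically significant and not clinically significant results if that is taken over the whole post-baseline period. SAP 6.8.2 does not say whether it is; Protocol 9.4.5 frames it by visit. As written, the general rules and the 6.8.2 condition conflict, and the literal reading can place a subject with a documented abnormality in the normal category.

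The number affected is unknown. The range under working depends on an assumed share and is not an estimate. Two facts are firm: two scheduled post-dose draws in Group A (plus early termination), and none for 114 of the 129 immunology-subset subjects.

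A reader might conclude that the trial's safety reporting as a whole is tilted toward normal. The documents do not support that: the affected table is a descriptive further-safety output in a trial with no hypothesis test, and the listings and adverse-event tables remain. It is a modest defect, worth correcting because the correction is cheap.

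**What to change.** Add to SAP 6.1.2 and 6.8.2:

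1. By-visit laboratory tables use scheduled visits.
2. The baseline-to-worst-post-baseline shift table, including its normal category, and any clinically significant or not clinically significant count over the whole post-baseline period use all post-baseline results, including unscheduled and repeat tests.
3. The denominator for these is the number of subjects with at least one post-baseline value for the parameter. The default in SAP 6.1.1, the full analysis set, would leave most of the 114 as missing.
4. A footnote states that post-baseline values in the non-transplant immunology subset are clinically triggered.
5. The text says how clinically indicated tests at scheduled visits and early-termination samples are treated.

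No new data are needed, because the values are already listed. The cost is a little programming and a possibly slightly less favourable table. In the non-transplant immunology subset, the tested subjects will be a selected and probably symptomatic few, so their percentages must not be read as rates for the subset or compared with Group A. That is why items 3 and 4 belong with item 2.
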